Statistical methods	
Primary and secondary endpoints:
 
A primary and 2 supplementary estimands will be defined for the primary endpoint, change in EASI from baseline to Week 16, in order to assess different clinical questions of interest.
 
 • The primary estimand for the primary endpoint will use the hypothetical strategy to handle the occurrence of pre-defined intercurrent events (initiation of rescue treatment and permanent discontinuation of IMP). • A first supplementary estimand will use the treatment policy and hypothetical strategies to account for the occurrence of intercurrent events. • A second supplementary estimand will use the composite and hypothetical strategies to handle the occurrence of intercurrent events. 
For the main analysis of the primary estimand, data observed after the occurrence of an intercurrent event will be excluded from the analysis. Missing data will be assumed to be MAR. The primary endpoint will be analyzed using an MMRM including treatment, visit, visit by treatment interaction terms, and region (Japan, non-Japanese countries) as factors, and adjusting for the baseline EASI score as a covariate. The covariance matrix will be assumed to have an unstructured form and the Kenward-Rodger approximation will be used to estimate the denominator degrees of freedom.
 
To explore the exposure-response relationship, the change in EASI score from baseline to Week 16 will be assessed based on an ANCOVA model including region as a factor and C_{trough} at Week 16 and baseline EASI score as covariates. Data observed after the occurrence of an intercurrent event will be excluded and missing data will be assumed to be MAR.

	The secondary endpoint, number of AEs from baseline to Week 16+3 days per subject, will be reported descriptively by treatment group.
Signatory investigator	PPD [REDACTED], MD PPD [REDACTED] [REDACTED] Hannover, Germany
Sponsor	LEO Pharma A/S, [name]

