14.1 Sample size

A total of 224 subjects, including 28 Japanese subjects will be randomised in a 4:3:3:4 ratio to the following treatment groups:

- LEO 152020 CCI [REDACTED]
- LEO 152020 CCI [REDACTED]
- LEO 152020 CCI [REDACTED]
- Placebo CCI [REDACTED]

The sample size is chosen, based on the results of a simulation, to approximately provide 90% power to reject the null hypothesis that the difference in the mean change in EASI score from baseline to Week 16 between the CCI [REDACTED] and placebo CCI [REDACTED] groups is greater than or equal to 0. The underlying assumptions for the simulation are presented below.

To approximate the power, 1,000 data sets with 224 subjects were generated based on the specified randomization scheme in Section 7.1. Each data set was analyzed based on the main analysis of the primary estimand specified in Section 14.3.8.1. The FWER for the analysis of each simulated data set was controlled based on the procedure specified in Section 14.3.7. The simulation made separate assumptions for the EASI response trajectory and rate of intercurrent events depending on baseline disease severity. For a given level of baseline disease severity, the assumed EASI response trajectory and rate of intercurrent events for the active arms, CCI [REDACTED] CCI [REDACTED] and CCI [REDACTED] are assumed to be the same.

For subjects with a baseline EASI score between CCI [REDACTED] the assumed response trajectory, in terms of the mean change in EASI score from baseline through Week 16, and the rate of intercurrent events, used to inform the simulation, are provided in Panel 15. The correlation matrix was assumed to have an AR(1) structure, with a correlation parameter equal to 0.65 and a residual variance assumed to be 18.9.

Panel 15: Assumed response trajectories and rates of intercurrent events by treatment group, for subjects with baseline EASI score between [CCI]

	Week 2	Week 4	Week 6	Week 8	Week 10	Week 12	Week 14	Week 16
Mean change from baseline to Week 16 in EASI score								
LEO 152020	CCI							
Placebo	CCI							
Proportion of subjects experiencing intercurrent event from the trial (%)								
LEO 152020	CCI							
Placebo	CCI							

Abbreviation: EASI = Eczema Area and Severity Index.

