14.3.8.1 Primary estimand

The primary estimand will use the *hypothetical strategy* to handle the occurrence of intercurrent events. The estimand attempts to quantify the effect of treatment, in the hypothetical scenario, where subjects do not permanently discontinue IMP for any reason and where rescue medication is not made available prior to Week 16.

For subjects observed to experience an intercurrent event, the potential outcomes under the envisioned hypothetical scenario, are assumed to follow the outcome distribution for subjects in the same treatment group, who did not experience an intercurrent event.

The primary estimand assesses the expected benefit of the treatment when adhering to the treatment regimen in the context of the specified hypothetical scenario.

Main analysis

Data collected after permanent discontinuation of IMP, regardless of reason, or the initiation of rescue treatment will be excluded from the analysis and "treated as missing".

The endpoint will be analyzed using a MMRM. The model will include treatment, visit, visit by treatment interactions, and region (Japan, non-Japanese countries) as factors and be adjusted for the baseline EASI score as a covariate. The covariance matrix will be assumed to have an unstructured form and the Kenward-Roger approximation will be used to estimate the denominator degrees of freedom. Missing data, including data excluded due to the occurrence of an intercurrent event, is assumed to be MAR. The estimated LS-mean treatment differences, based on the observed margins, will be presented with 95% CIs and nominal p-values at each visit. The primary comparison is the treatment difference at Week 16, between the CCI and placebo groups.

Sensitivity analysis

The following sensitivity analyses will assess the robustness of the results of the main analysis with respect to the underlying statistical assumptions. The impact of the missing data assumptions on data excluded after the occurrence of an intercurrent event/due to the pandemic will not be considered in the sensitivity analyses, as the MAR assumption is aligned with the envisioned hypothetical scenario.

- Sensitivity analysis 1: Exclusion of subjects with monotone missing data at Week 1

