Subjects with monotone missing data from Week 1 onwards are automatically excluded from the analysis. Although under the MAR assumption, the estimator of the treatment effect based on a likelihood analysis of a MMRM is unbiased, such exclusions run contrary to the intent of the FAS.

This sensitivity analysis will assess the robustness of the results of the main analysis with regards to the exclusion of subjects with no observed post-baseline EASI assessments. The analysis will include all randomized subjects regardless of whether a subject has observed post-baseline EASI score assessments. To assess the impact of excluding subjects with no post-baseline EASI score assessments from the analysis, the LS-mean treatment contrasts for the MMRM specified in the main analysis, will be estimated using the mean baseline EASI score and the proportion of subjects from each region based on the FAS.

- Sensitivity analysis 2: Functional form of the baseline EASI score covariate

This sensitivity analysis will assess the robustness of the results of the main analysis with respect to the assumed linear relationship between the mean change in EASI score from baseline to Weeks 1-16 and the baseline EASI score. Additional details for each sensitivity analysis will be specified in the SAP.

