For each of the 1,000 complete datasets, the change in EASI score from baseline to Week 16 will be analyzed using an ANCOVA model including treatment, and region (Japan, non-Japanese countries) as factors, and baseline EASI score as a covariate. The pooled estimates of the difference in the LS-mean change from baseline to Week 16, based on the observed margins, along with the associated 95% CIs and nominal p-values will be presented. Pooled inference will be based on applying Rubin's rules to the estimates and standard errors from the ANCOVA analysis of the imputed datasets.

Sensitivity analysis

A tipping point analysis will be performed based on implementing a delta-adjusted multiple imputation approach. The delta-adjusted imputation approach allows for missing data to be imputed under the MNAR assumption. Heuristically, the imputation strategy, adjusts/shifts the parameters of the MAR distribution based on the value of a numeric offset term, denoted by delta. The tipping point analysis will adjust the values of the parameters in the MAR distribution representing the mean change in EASI score from baseline to Weeks 1-16. The analysis will assess how robust the results of the main analysis are to varying departures from the MAR assumption within each active treatment group.

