14.3.10 Analysis of exploratory endpoints

Continuous endpoints

- EASI at each visit from Week 1 to Week 16.
- SCORAD at each visit from Week 1 to Week 16.
- Change in ADSD score (weekly average) from baseline to Week 16.
- Change in each ADSD individual symptom score (weekly average) from baseline to Week 16.

will be summarized descriptively at each visit by treatment group and will be analyzed using an MMRM. The model will include treatment, visit, visit by treatment interaction terms, region (Japan, non-Japanese countries), and baseline disease severity (EASI score at baseline ≤ 16 and ≥ 16.1) as factors and adjust for the baseline value of the endpoint of interest as a covariate. For the analysis of the EASI score at each visit, the baseline disease severity factor will be excluded from the MMRM in order to avoid introducing a discontinuity in the relationship between the post-baseline EASI scores and the baseline EASI score. The model

will use an unstructured covariance matrix, and the Kenward-Roger approximation to estimate the denominator degrees of freedom. The SAP will specify alternative structures for the covariance matrix, to be used in case of non-convergence. For these endpoints, data collected after permanent discontinuation of IMP or after initiation of rescue medication will be excluded from the analysis and 'treated as missing'. Missing data will be assumed to be MAR. The estimates will be presented with 95% CIs and nominal p-values at each visit.

Binary endpoints

- Having a decrease in EASI of at least 50% (EASI 50) from baseline to Week 16.
- Having a decrease in EASI of at least 75% (EASI 75) from baseline to Week 16.
- Having a decrease in EASI of at least 90% (EASI 90) from baseline to Week 16.
- Having vIGA-AD of 0 (clear) or 1 (almost clear) at Week 16.
- Having a decrease in vIGA-AD of at least 2 points from baseline to Week 16.
- Having a decrease in ADSD **CCI** score (weekly average) of at least 4 points from baseline to Week 16 in subjects with ADSD **CCI** score ≥ 4 at baseline.

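### The primary MMRM fits one baseline-EASI slope across all nine post-baseline visits; a baseline-by-visit term would protect precision at Week 16 at almost no cost

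*Combined protocol and SAP*

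**What the plan says.** Section 14.3.8.1, Main analysis, gives the mean structure: "The model will include treatment, visit, visit by treatment interactions, and region (Japan, non-Japanese countries) as factors and be adjusted for the baseline EASI score". The synopsis gives the same model: "The primary endpoint will be analyzed using an MMRM including treatment, visit, visit by treatment interaction terms, and region". Neither has a baseline-by-visit term. The covariance is unrestricted: "The covariance matrix will be assumed to have an unstructured form". The result that counts is a single visit: "The primary comparison is the treatment difference at Week 16". That contrast is also the gatekeeper for the other two active regimens (Section 14.3.7).

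Panel 2 schedules nine post-baseline EASI assessments, at Weeks 1, 2, 4, 6, 8, 10, 12, 14 and 16. One baseline slope therefore serves all nine.

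Three other places bear on the point:

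- Sensitivity analysis 2 in Section 14.3.8.1 examines the "assumed linear relationship between the mean change in EASI score from baseline to Weeks 1-16 and the baseline EASI score". It is described as a check of linearity in baseline. Its details are left to the SAP.
- For the first supplementary estimand, "the change in EASI score from baseline to Week 16 will be analyzed using an ANCOVA model including treatment, and region", with baseline EASI as covariate. The second supplementary estimand uses the same kind of model. A single-visit ANCOVA has its own Week 16 slope.
- The exploratory MMRMs in Section 14.3.10 likewise "adjust for the baseline value of the endpoint of interest as a covariate", again without a visit interaction.

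**The concern.** Change from baseline cannot exceed the baseline score in size, and eligible scores span 7.1 to 50. The plan itself measures response as a proportion of baseline (EASI 50, 75, 90). If improvement is roughly proportional to baseline, the slope of change on baseline is minus the mean proportional improvement, so it becomes more negative as response builds from Week 1 to Week 16. The power section also treats response as severity-dependent: "The simulation made separate assumptions for the EASI response trajectory and rate of intercurrent events depending on baseline disease severity". The actual slopes cannot be seen, because Panels 15 and 16 are redacted.

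A shared slope is a weighted average over visits. If the true slope steepens, that average is too shallow at Week 16, and part of the outcome variance that baseline could explain stays in the Week 16 residual. The standard error and p-value of the primary contrast then carry that extra variance.

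**Working it through.** **Inputs from the documents.** 224 subjects allocated 4:3:3:4, which is 64/48/48/64; randomization stratified by baseline EASI (Section 9.3.1); nine visits (Panel 2); two-sided 5% (Section 14.3.1); AR(1) correlation 0.65, stated for one severity stratum only (Section 14.1); power 90.8% for the primary contrast and 85.3% marginal or 79.4% after Hochberg for the others (Panel 17).

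**Assumptions, not given in the documents.** Baseline SD 10; Week 16 residual SD 9; baseline slope -0.1 at Week 1, moving linearly in time to -0.3, -0.4 or -0.5 at Week 16; residual SD either constant or doubling from Week 1 to Week 16.

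**1. Panel 17.** The 90.8% cannot be derived, because effect sizes and event rates are redacted. Its consistency can be checked. At 64 vs 64 it implies a standardized effect of (1.960 + 1.329) × √(2/64) = 0.581. At 48 vs 64 that effect gives 86.1% (stated 85.3%), and 79.3% after gatekeeping and Hochberg by simulation (stated 79.4%). The panel is coherent.

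**2. Shared slope.** With an unstructured covariance S and visit slopes b, the fitted common slope is b* = 1'S⁻¹b / 1'S⁻¹1. Under AR(1) 0.65 with constant variance, Weeks 1 and 16 each have weight 1/(2 + 7 × 0.35) = 1/4.45 = 0.225, and each interior visit 0.35/4.45 = 0.079. If the residual SD doubles in equal steps by visit, Week 1 has about 0.48 and Week 16 about 0.09.

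**3. Excess variance at Week 16.** Model variance factor = 1 + Var(X)(b₁₆ - b*)²/σ₁₆². Worked case, -0.1 to -0.5 with constant SD:

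- The weighted mean of (week - 1)/15 is 0.0787 × 49/15 + 0.225 = 0.482, so b* = -0.1 - 0.4 × 0.482 = -0.293.
- The gap is 0.207, and the factor is 1 + 100 × 0.207²/81 = 1.053.
- The model SE is √1.053 = 1.026 times what it could be.

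Stratified randomization limits the real chance imbalance to within-stratum variation, taken as 41% of Var(X). The sampling SE factor is therefore √(1 + 0.41 × 0.053) = 1.011.

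**4. Simulation.** 10,000 trials per scenario, complete data, region omitted, with the plan's model and the interaction model fitted to the same data.

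| Week 16 slope | Residual SD | b* | Model SE excess, formula | Model SE excess, simulated | Sampling SE excess, simulated |
|---|---|---|---|---|---|
| -0.3 | constant 9 | -0.196 | 0.7% | 0.6% | 0.2% |
| -0.4 | constant 9 | -0.244 | 1.5% | 1.5% | 0.6% |
| -0.5 | constant 9 | -0.293 | 2.6% | 2.7% | 1.1% |
| -0.3 | 4.5 to 9 | -0.150 | 1.4% | 1.4% | 0.5% |
| -0.4 | 4.5 to 9 | -0.176 | 3.1% | 3.2% | 1.2% |
| -0.5 | 4.5 to 9 | -0.201 | 5.4% | 5.6% | 2.2% |

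With the effect set so that the plan's model has 90.8% power, the interaction model has 91.1% to 91.9% (constant SD) or 91.4% to 93.0% (growing SD). Type I error is 4.4% to 4.9% for the plan's model and 4.9% with the interaction. With a flat slope of -0.4 the model SEs are 1.589 and 1.591, and power is 90.8% for both.

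By formula, a slope that plateaus lowers the model SE excess to 0.4% to 1.6% (constant) or 1.1% to 4.3% (growing). A residual SD of 7 raises it to at most 4.5% or 9.2%.

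**5. Dropout.** A second, smaller simulation (400 runs per scenario; slope -0.15 to -0.5; residual SD 4 to 9; approximate degrees of freedom rather than Kenward-Roger) gave model SE ratios, plan to interaction, of 1.044 with no dropout, 1.045 with 15% MCAR dropout and 1.046 with MAR dropout. Power, plan vs interaction, was 88.7% vs 91.0%, 84.3% vs 86.0% and 81.8% vs 81.5%. The last pair is within simulation error. Across steepening scenarios mean estimates lay between -5.14 and -5.33 against a true -5.2, and under the null they were about -0.02 for both models.

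**The case against.** The strongest reply is that nothing is broken. The estimator shows no material bias, type I error is not inflated, and the trial was sized by simulating this same model, partly on data resampled from earlier phase 3 trials. Any loss present in those data is already inside the 90.8%. All of that stands.

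It also stands that the steepening slope and its size are assumptions, that the sampling-SE gain is small (0.2% to 2.2%) because randomization is stratified by severity, and that no power gain was visible in the moderate MAR scenario. The model SE is still what drives the p-value and confidence interval, and it fell by a similar proportion with and without dropout.

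A further argument is that most of the gain lies within the Monte Carlo margin of the sponsor's 1,000 data sets: √(0.908 × 0.092/1000) = 0.9%, so about ±1.8 points. That margin describes uncertainty in the stated 90.8%. It does not apply to the difference between two models fitted to the same data.

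Sensitivity analysis 2 might, once detailed in the SAP, let the slope vary by visit. Even so, a sensitivity analysis would leave the primary p-value unchanged. Finally, the supplementary ANCOVAs have a Week 16 slope simply because they model one visit. They set no rule that the MMRM breaks, but they do mean that the primary analysis has the more restrictive baseline adjustment at the same time point.

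**Conclusion.** The concern holds as a precision point. The primary model constrains the baseline slope to be constant over nine visits, nothing in the protocol text relaxes this, and the constraint can only cost precision at the visit that matters. Under the stated assumptions the Week 16 model SE is about 0.6% to 2.7% larger than necessary with constant residual variance and 1.4% to 5.6% larger with growing variance, worth a few tenths of a point to about two points of power. With a flat slope the loss is nil. The exact size cannot be fixed from the documents, since visit-specific slopes, baseline SD and Week 16 residual SD are not given. The plan's validity and its stated 90.8% are unaffected. The reason to act is the asymmetry: a modest likely gain against a negligible cost.

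**What to change.** Add a baseline EASI by visit interaction to the primary MMRM in Section 14.3.8.1 and in the synopsis. For consistency, add own-baseline by visit to the Section 14.3.10 MMRMs with many post-baseline visits (EASI, SCORAD, ADSD); the calculations above cover only the primary endpoint. Do not carry it to EQ-5D-5L, which has one scheduled on-treatment post-baseline visit. State in the SAP whether Sensitivity analysis 2 concerns linearity, constancy over visits, or both.

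The cost is one model term, that is 8 extra parameters (nine slopes instead of one) with 224 subjects, plus protocol or SAP wording. Section 14.3.1 already provides for finalizing the SAP before the randomization code is broken, so the term can be prespecified without unblinding. Panel 17 was simulated with the present model. It can be rerun, or kept with a note that it refers to the model without the interaction, since the simulated cost under a flat slope is about 0.1% of SE with no visible loss of power.

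### Sensitivity analysis 1 of the primary estimand, as written, reproduces every treatment difference exactly, so it cannot test the exclusion of subjects with no post-baseline EASI

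*Combined protocol and SAP*

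**What the plan says.** Section 14.3.8.1 specifies the main analysis as an MMRM: "The model will include treatment, visit, visit by treatment interactions, and region (Japan, non-Japanese countries) as factors", plus baseline EASI as a covariate, an unstructured covariance matrix and Kenward-Roger degrees of freedom. For reporting, "The estimated LS-mean treatment differences, based on the observed margins, will be presented with 95% CIs and nominal p-values at each visit".

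The same section then explains the reason for Sensitivity analysis 1: "Subjects with monotone missing data from Week 1 onwards are automatically excluded from the analysis", and "such exclusions run contrary to the intent of the FAS". The stated aim is to assess how robust the main results are to that exclusion, with all randomized subjects included. The method is one sentence: "the LS-mean treatment contrasts for the MMRM specified in the main analysis, will be estimated using the mean baseline EASI score and the proportion" belonging to each region, both taken from the FAS. No refit, imputation or arm-specific margin is mentioned. The section closes its sensitivity analyses with "Additional details for each sensitivity analysis will be specified in the SAP"; the text at hand gives no such details.

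Two neighbouring statements limit what else is tested. "The impact of the missing data assumptions on data excluded after the occurrence of an intercurrent event/due to the pandemic" is declared outside the sensitivity analyses, because missing at random (MAR) matches the hypothetical scenario. Sensitivity analysis 2 concerns only the "Functional form of the baseline EASI score covariate".

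**The concern.** A sensitivity analysis is informative only if it could have disagreed with the main result. This one changes the covariate values at which LS-means are evaluated, but keeps the fitted model. Subjects without any post-baseline EASI enter the margins and add nothing to the likelihood. If the margins drop out of the treatment differences, the analysis returns the main result on precisely the quantity the plan names, the treatment contrasts.

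At stake is interpretation. A reader who sees identical estimates, intervals and p-values could take them as evidence that the exclusions did not matter, when agreement was guaranteed by construction.

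**Working it through.** **Inputs.** Model terms and margins: Section 14.3.8.1. Sample size 224 with 28 Japanese subjects, allocation 4:3:3:4: Section 14.1. The plan states no figure for this analysis, so there is none to reproduce.

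**Algebra.** For arm j and visit k, with region proportions p_r and mean baseline m:

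LSM(j,k) = mu + trt_j + visit_k + (trt x visit)_jk + sum_r p_r * region_r + b * m

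LSM(j,k) - LSM(0,k) = trt_j - trt_0 + (trt x visit)_jk - (trt x visit)_0k

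Neither p_r nor m remains. The contrast vector has zeros for region and baseline whichever margins are used. Subjects with no post-baseline response add no rows to the REML likelihood, so the estimates, their covariance and the Kenward-Roger adjustment are also unchanged. The result holds for any data.

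**Numerical check.** One simulated trial: 224 subjects (placebo 64; active 64, 48, 48), 28 Japanese, nine post-baseline visits, unstructured REML. Twelve subjects with severe baseline disease were given no post-baseline EASI. Means, variances and dropout are assumed. Intervals and p-values are Wald.

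- Margins, 212 analysed subjects: mean baseline 25.21, Japan 12.26%.
- Margins, FAS of 224: mean baseline 26.27, Japan 28/224 = 12.50%.

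| Week 16 | Main margins | FAS margins | Change |
|---|---|---|---|
| Placebo LS-mean | -5.352 | -5.775 | -0.423 |
| First active LS-mean | -8.442 | -8.865 | -0.423 |
| Difference, active 1 | -3.08981960 (SE 1.50181599) | -3.08981960 (SE 1.50181599) | 0 |
| Difference, active 2 | -2.37074642 (SE 1.53687609) | -2.37074642 (SE 1.53687609) | 0 |
| Difference, active 3 | -1.16090020 (SE 1.55999841) | -1.16090020 (SE 1.55999841) | 0 |

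For active 1 the 95% CI is -6.033 to -0.146 and p = 0.0397 under both sets of margins.

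**Positive control.** With a treatment-by-baseline term added to the same data, the active 1 difference moves from -3.002 (SE 1.509, p = 0.0466) to -3.049 (SE 1.512, p = 0.0438). The check can detect a change when the model allows one.

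**Repetition.** In a second set of 120 simulated trials, with 27 contrasts each (3 active arms x 9 visits), the largest difference in estimate, SE or contrast vector was 0. Per-arm LS-means moved by 0.001 to 0.123 points.

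**What the replacement would do.** The same 120 trials (four assumed missing-data patterns, 30 trials each) used AR(1) correlation 0.65 and variance 18.9, which Section 14.1 gives for one severity stratum, applied here to everyone. Trajectories are assumed. MMRM SEs were 0.825 to 0.841.

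- Multiple imputation by arm with no delta shift: the Week 16 difference departs from the MMRM by -0.009 to +0.046 on average (mean absolute 0.07 to 0.10, largest 0.29, Monte Carlo error about 0.03). The SE is 6 to 7% larger.
- Delta shift: with n of N subjects in an active arm shifted, the difference moves by about delta * n/N. One of 64 with no post-baseline EASI and a delta of 5 gives 5/64 = 0.078; the simulation gave 0.076. At that rate a shift of one SE needs a delta of about 5 * 0.825/0.076 = 54 EASI points.

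**The case against.** **The SAP may supply the content.** The plan defers details, and Section 14.3.1 has the SAP finalized before the code is broken. This stands in part: the defect is shown for the text as written, and one cannot say that the final report will contain an empty analysis. But the operation already stated fixes the outcome, so the SAP can cure it only by adding to or replacing it.

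**Other margins or interactions may be intended.** Arm-specific margins, or a treatment interaction with baseline or region, would break the identity. The text specifies neither. Baseline-by-visit or region-by-visit terms would still cancel.

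**The group is small and mostly exempt.** This stands. FAS subjects take their first dose at the site (Section 9.2), and EASI is due at nine later visits (Panel 2). A subject who never returns is treated as withdrawn and lost to follow-up (Section 10.5). Both are recorded reasons for permanent discontinuation of IMP (Section 10.2), which is an intercurrent event. A subject kept on treatment through remote visits under Appendix 9 has no investigator efficacy assessment, and those gaps are pandemic-related. Most subjects with no post-baseline EASI therefore fall under the exemption, and few or none may be left for a delta shift.

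**The aim is fidelity to the FAS, not a test of MAR.** This also has force. The plan notes that its estimator is unbiased under MAR. A reader might infer that the primary estimand needs a general missing-not-at-random analysis, including sporadic Week 16 gaps. That goes beyond what Sensitivity analysis 1 sets out to do. The exemption is a stated design choice, and Section 14.3.8.2 already has a tipping point under another estimand.

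**The replacement changes the model too.** Agreed: a difference from the main result would mix the effect of the exclusion with that of moving from MMRM to imputation plus ANCOVA.

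**Conclusion.** The point holds for the protocol wording. Sensitivity analysis 1 changes each treatment difference, SE, CI and p-value by exactly 0, for any data, and moves only arm-level LS-means. It cannot assess whether the treatment effect is robust to excluding subjects with no post-baseline EASI. This rests only on the stated model and common margins; the simulations illustrate it.

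A reader might infer that the primary result is biased or its test compromised. The documents do not support that: Section 14.3.7 bases hypothesis testing on the main analysis, which is untouched, and the excluded group is probably small. With so few values, a working replacement would probably also support robustness, but as a finding and not by construction. The imputation and delta figures depend on assumed counts and trajectories, because the documents give no counts and Panels 15 and 16 are redacted.

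**What to change.** In Section 14.3.8.1 and the matching SAP section:

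1. Replace the re-margining with an analysis of all FAS subjects: multiple imputation by arm using only data before intercurrent events, then the Week 16 ANCOVA and Rubin's rules as in Section 14.3.8.2.
2. Report by arm the number of subjects with no post-baseline EASI, and how many of them had an intercurrent event or pandemic-related missingness.
3. Apply a delta shift only to subjects with no post-baseline EASI who fall outside the exemption in Section 14.3.8.1. If there are none, say so. Leave the exemption itself unchanged.
4. If the margin-based analysis is kept, state that it affects arm-level LS-means only and that agreement of the differences is not evidence of robustness.

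The cost is one protocol paragraph, the SAP text and one or two tables that must be reported whatever they show. The methods exist in Section 14.3.8.2, but the imputation model must be refitted without post-event data. The SE of this sensitivity analysis will be slightly larger (about 6 to 7% in the simulation), and the report should say that part of any difference reflects the change of model.
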